6.3. Measures to Minimize Bias: Randomization and Blinding

In order to minimize bias in measurement of the primary efficacy endpoint (height), the anthropometrist will be blinded to dose assignment. There will be no additional blinding.

6.3.1. Allocation to Study Intervention

Allocation of participants to treatment groups will proceed through the use of an IRT system. The site personnel (study coordinator or specified designee) will be required to enter or select information including, but not limited, to the user's ID and password, the protocol number and the participant number. The site personnel will then be provided with a treatment assignment, randomization number and Dispensable Unit (DU) or container number when study intervention is being supplied via the IRT system. The IRT system will provide a confirmation report containing the participant number, randomization number and DU or container number assigned. The confirmation report must be stored in the site's files.

This is a partially blinded study with open-label supplies. Potential bias will be reduced by the following: central randomization, and an otherwise uninvolved third party will be responsible for conducting assessments related to primary efficacy endpoint and anthropometric secondary endpoints. Study intervention will be dispensed at the study visits summarized in the [SoA](#).

The study -specific IRT reference manual and IP Manual will provide the contact information and further details on the use of the IRT system.

6.3.2. Other Measures to Minimize Bias

Anthropometric data will only be collected by appropriately trained individuals at the trial site and in accordance with the anthropometric measurement manual. All sites will follow a consistent, structured and documented training program. This will occur prior to trial start, through regular refresher training and at targeted retraining based on analysis of measurement data consistency at the site. Training and assessment of competency will be performed by dedicated anthropometric training staff contracted by the sponsor.

Sites will be required to make all efforts to have the same anthropometrist at each visit for each participant (longitudinal consistency) and between participants (cross-sectional consistency). As well as following the specific procedures for measurement laid out in the measurement manual, sites will be provided with the same (or exactly equivalent) equipment across all sites and will follow the specific calibration procedures. The anthropometrist should remain blinded to dose assignment.

If the anthropometrist becomes unintentionally unblinded then they should continue to act as the anthropometrist for that participant since a change in anthropometrist is known to be a significant source of variability in measurement data. If any measures are taken following unblinding of the anthropometrists, this will be recorded in the eCRF. All blinded & unblinded measurements collected will be analysed, with further details available in the SAP.

6.4. Study Intervention Compliance

When participants are dosed at the site, they will receive study intervention directly from the investigator, a designee (under medical supervision) or from the caregiver under supervision of site staff. The date, time, injection site and volume of each dose administered in the clinic will be recorded in the source documents and recorded in the eCRF. The same data will be collected in the dosing diary when administered at home. The dose of study intervention and study participant identification will be confirmed at the time of dosing by a member of the study site staff other than the person administering the study intervention.

The site will complete the required dosage Preparation Record located in the IP Manual. The use of the Preparation Record is preferred, but it does not preclude the use of an existing appropriate clinical site documentation system. The existing clinical site's documentation system should capture all pertinent/required information on the preparation and administration of the dose. This may be used in place of the Preparation Record after approval from the sponsor and/or designee.

When participants are dosed at home, compliance will be monitored by completion of a dosing diary by the caregiver which will record date, time, injection site and volume of dose administration. This diary will be reviewed by the site staff. Where home nursing have supported home dosing then this will be recorded.

If poor compliance is identified by site staff then additional training and support will be provided to the caregivers.

6.4.1. Participant Compliance and Home Administration

Caregivers will be permitted to administer reciferecept once they have demonstrated an understanding of the preparation and administration process at the site. Confirmation of a caregiver's ability to perform preparation and administration must be documented in the site file. For administration of reciferecept at home, compliance and any injection site reactions will be captured and completed by the caregiver by completing the dosing diary. Caregivers should contact the site immediately in the event of any potential injection site reactions.

Caregivers will administer treatment from the point of which they have demonstrated the capability to do so (as stated above) until the end of dosing. Prior to administration at home, sites must ensure caregivers are trained on IP administration and storage per the dosing diary. Dosing between planned clinic visits may be administered by investigational site staff until the respective caregiver has been properly trained in administration. Sites should follow -up (eg, via phone call) to ensure compliance with administration instructions, where necessary. Clinic administration of study intervention can be readministered at any time where home dosing is deemed not feasible or inappropriate. Caregivers will be supported to reinstitute home dosing where appropriate.

6.5. Concomitant Therapy

6.5.1. Prohibited During the Study

Participants may not receive any medication or procedure that may affect the growth of the long bones. This includes human growth hormone (or related medicines such as IGF-1) and surgical/interventional procedures such as limb lengthening.

Participants cannot undergo surgical procedures of the bone during the course of the trial. This includes limb lengthening, guided growth (eg, 8 plates), tibial osteotomies, spinal surgery, neurosurgical procedures or ear, nose, and throat (ENT) bone procedures.

6.5.2. Prohibited Prior Treatments

Participants who have received prior human growth hormone or related products will not be eligible to participate.

Any participant that has previously received an investigational medicinal product for the treatment of achondroplasia is not eligible to participate.

Past receipt of any investigational medicinal product that could affect growth may not participate.

Receipt of any other investigational medicinal product (not covered above) in the last 30 days or 5 half-lives (whichever is longer) is prohibited.

Participants may not have previously undergone any limb-lengthening surgery.

6.6. Dose Modification

The decision to proceed to the next enrollment block of reciferecept will be made by the study team based on safety, tolerability, and preliminary PK data obtained in at least 3 participants at each new dose and age bracket. The PK data from Block A participants aged ≥ 6 to < 11 years will be integrated into the PopPK model developed using healthy adult PK data, to then confirm the dosing recommendations in younger age sub-cohorts (≥ 2 to < 6 years and ≥ 3 months to < 2 years). It is anticipated that the relationship between body weight and PK will be well characterized at this stage and no further dosing adjustment may be required for the youngest age group (≥ 3 months to < 2 years). However, to minimize the uncertainty in

children aged ≥ 3 months to <2 years, PK data collected in the ≥ 2 to <6 -years cohort will be used to evaluate consistency with the predicted dose-concentration relationship. This review will be performed at the following times:

Block A to B	Review after all block A participants (n=6, all aged 6-10y) have completed D29
Block B to C	Review once 2-6y participants (n=4) and 3 high dose 6-10y participants have completed D29
Block C to D	Review once all ≥ 3 months -2y participants (n=4) and 3 high dose 2-6y participants have completed D29

6.6.1. Rules for Progression to Next Enrollment Block

The eDMC will meet after block A participants have received 4 weeks of study intervention (completed D29) to review safety and PK data. They will make recommendations on dose levels and progression to block B.

Progression to blocks C and D, will occur without eDMC review if NONE of the following criteria are met:

- Serious Adverse Reaction (IMP-related SAR);
- ≥ 2 participants affected by the same moderate/severe study intervention-related AE;
- ≥ 2 participants affected by an AE of hypersensitivity to study intervention;
- ≥ 2 participants with severe ISRs;
- ≥ 2 participants with ISR leading to withdrawal of study intervention.

If any of these criteria are met then the eDMC must be convened to make a decision on progression to the next enrollment block. In addition, no further participants will be enrolled at that dose (or higher) until eDMC recommendation has been issued.

A sentinel approach will be used in recruiting those aged 2- <6 years in block C such that n=2 at high dose will be dosed followed by a 2-week delay before further dosing occurs in that age group.

The dosing schedule may also be adjusted by the eDMC to expand a dosing cohort to further evaluate safety and/or PK findings at a given dose level or to amend the doses to be studied in each enrollment block. The study procedures for these additional participant(s)/cohort(s) will be the same as that described for other study participants/cohorts.

In addition, following evaluation of the overall benefit:risk assessment at the interim analysis, the dose levels may be adjusted. If a new dose level is introduced then this will form a new cohort (minimum n=15) of treatment naïve participants. Previously treated subjects at a discontinued dose will be moved to the next lowest continuing dose.

Any dose modifications will not exceed the current maximum dose (1.5mg/kg once-daily) without submission and approval of a protocol amendment.

6.7. Intervention After the End of the Study

No intervention will be provided to study participants at the end of the study, however participants will be offered to roll over into an open-label extension study.

7. DISCONTINUATION OF STUDY INTERVENTION AND PARTICIPANT DISCONTINUATION/WITHDRAWAL

7.1. Discontinuation of Study Intervention

In rare instances, it may be necessary for a participant to permanently discontinue study intervention (definitive discontinuation). Reasons for definitive discontinuation of study intervention include the following:

- Non-compliance with study intervention;
- Pregnancy;
- Withdrawal of consent by parent/guardian;
- Investigator decision to withdraw;
- Death.

The decision to withdraw the participant from the study ultimately lies with the investigator. For example occurrence of any clinically relevant sign or symptom that, in the opinion of the Investigator (or designee), warrants subject withdrawal. Additionally if a subject experiences a serious or intolerable AE that prevents them from continuing with study participation such as severe injection site reaction or hypersensitivity, this would be expected to lead to withdrawal.

Study intervention will be discontinued if the investigator considers that it is in the participants best interest to initiate any of the prohibited treatments described in [Section 6.5.1](#).

If study intervention is definitively discontinued, the participant will not remain in the study for further evaluation. See the [SoA](#) for data to be collected at the time of discontinuation of study intervention.

ECG Changes

ECG will be collected at baseline and at Day 4, then only repeated if, in the opinion of the investigator, they are clinically indicated. If a clinically significant finding is identified (including, but not limited to, changes from baseline in QTcF after enrollment), the investigator or qualified designee will determine if the participant can continue in the study and if any change in participant management is needed. This review of the ECG printed at the time of collection must be documented. Any new clinically relevant finding should be reported as an AE. Further details of potentially significant ECG changes can be found in [Appendix 6](#).

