7.2. Participant Discontinuation/Withdrawal From the Study

A participant may withdraw from the study at any time at his/her own request. Reasons for discontinuation from the study include the following:

- Refused further follow-up;
- Lost to follow-up;
- Death;
- Study terminated by sponsor.

At the time of discontinuing from the study, if possible, an early termination visit should be conducted. See the [SoA](#) for assessments to be collected at the time of early termination and follow-up and for any further evaluations that need to be completed.

The early termination visit applies only to participants who are enrolled/randomized and then are prematurely withdrawn from the study. Participants and/or their parent/guardian should be questioned regarding their reason for withdrawal.

If a participant withdraws from the study, he/she may request destruction of any remaining samples taken and not tested, and the investigator must document any such requests in the site study records and notify the sponsor accordingly.

If the participant withdraws from the study and also withdraws consent (see [Section 7.2.1](#)) for disclosure of future information, no further evaluations should be performed and no additional data should be collected. The sponsor may retain and continue to use any data collected before such withdrawal of consent.

Lack of completion of all or any of the withdrawal/early termination procedures will not be viewed as protocol deviations so long as the participant's safety was preserved.

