7.2.1. Withdrawal of Consent

Participants who request to discontinue receipt of study intervention will remain in the study and must continue to be followed for protocol-specified follow-up procedures. The only exception to this is when a participant specifically withdraws consent for any further contact with him or her or persons previously authorized by the participant to provide this information. Participants should notify the investigator in writing of the decision to withdraw consent from future follow-up, whenever possible. The withdrawal of consent should be explained in detail in the medical records by the investigator, as to whether the withdrawal is only from further receipt of study intervention or also from study procedures and/or posttreatment study follow-up, and entered on the appropriate CRF page. In the event that vital status (whether the participant is alive or dead) is being measured, publicly available information should be used to determine vital status only as appropriately directed in accordance with local law.

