9.1.1. Estimands

The primary efficacy estimand will be the population treatment effect of the mean change-from-baseline of a continuous response (ie, height growth) at month 12 irrespective of IP compliance. Increase in height growth above expected growth in reference population, a co-primary endpoint, is defined as the height growth in the achondroplasia reference population +50%. Intercurrent event for the efficacy estimand: withdrawal and all events leading missing data will be excluded from efficacy analysis and will not have their data imputed. The population-based treatment effect will be the mean change-from-baseline at 12 months.

The secondary estimand will be the population treatment effect of the mean change from baseline of a continuous response, defined as the decline in the difference of arm span to standing height. Intercurrent event for the efficacy estimand: withdrawal and all events leading missing data will be excluded from efficacy analysis and will not have their data imputed.

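### Protocol 7.1 and 7.2.1 give opposing instructions on follow-up after stopping drug, so Month 12 height may go unmeasured in children whom the 9.1.1 estimand appears to count

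*Protocol*

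**What the plan says.** **Protocol 7.1.** The first listed reason for definitive discontinuation is "Non-compliance with study intervention". The section then says: "If study intervention is definitively discontinued, the participant will not remain in the study for further evaluation". It describes definitive discontinuation as rare.

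**Protocol 7.2.1.** "Participants who request to discontinue receipt of study intervention will remain in the study and must continue to be followed for protocol-specified follow-up procedures". This does not apply to a participant who withdraws consent for any further contact.

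**Protocol 9.1.1 (repeated in the synopsis).** The primary efficacy effect is the mean change in height "at month 12 irrespective of IP compliance". The same paragraph adds that "withdrawal and all events leading missing data will be excluded from efficacy analysis and will not have their data imputed".

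**Protocol 7.2 and the Schedule of Activities.** "At the time of discontinuing from the study, if possible, an early termination visit should be conducted". Anthropometry is scheduled at that visit, but leaving its procedures undone is not a protocol deviation provided safety was preserved.

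**Protocol 6.4.** "If poor compliance is identified by site staff then additional training and support will be provided to the caregivers".

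**SAP.** Section 2.1.1 repeats the exclusion of withdrawals and missing-data events and does not mention compliance. Section 6.1.1.1 labels the strategy hypothetical and drops measurements taken after drug has stopped. Appendix 1, for the same main analysis, keeps all collected data whatever intercurrent events occur.

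**The concern.** A family that asks to stop injections, without refusing follow-up, falls under both 7.1 and 7.2.1. One site could discharge the child and another could keep measuring, and each would be following the protocol. For a child whom the investigator stops for non-compliance, the conflict is between 7.1, which ends evaluation, and the 9.1.1 clause that counts Month 12 growth whatever the compliance.

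At stake is whether a co-primary endpoint is measured in children who come off drug. An analysis rule can still be changed before database lock; a missed Month 12 visit cannot be recovered. Stopping could also differ by dose, because the regimens are weekly, twice weekly and daily. The documents give no stopping rates by dose, so this is plausible rather than shown.

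**Working it through.** **1. The plan's own figures.** Protocol 9.2 gives 18 randomised per dose to obtain 15, variability 0.15, an effect of 50% above reference, one-sided 0.017, and power over 90%. I read 0.15 as the SD of the growth ratio H (observed over expected growth). The protocol does not state the scale, so this is an assumption.

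- One-sample one-sided t-test of H against 1.0 with n = 15: noncentrality = (0.5 / 0.15) × √15 = 12.9, power > 0.9999. The stated lower bound is met with room to spare; n = 4 already gives 96%.
- Planned loss: 3/18 = 16.7% per dose, from all causes.

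**2. What the text does with each kind of child.**

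| Situation before Month 12 | 7.1 | 7.2.1 | 9.1.1 |
|---|---|---|---|
| Family asks to stop drug, accepts follow-up | leaves | stays | counted by the compliance clause, removed by the withdrawal clause |
| Investigator stops drug for non-compliance | leaves | not clearly covered | as above |
| Poor compliance, drug continued | not triggered | not triggered | counted, and measured |
| Consent to all further contact withdrawn | leaves | leaves | excluded |

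The first two rows are the problem.

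**3. Whether anything else supplies the height.**

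- The early-termination height is taken when the child leaves. Under SAP Appendix 2.1 it is a Month 12 value only on Days 346 to 366.
- The sensitivity analysis uses the per-protocol set, which requires complete data through Month 12, so it omits the same children.
- The SAP's mixed model uses Months 3, 6, 9 and 12. A child who stops at Month 8 still contributes Months 3 and 6. The model cannot observe growth after stopping, and predicts it from children still on drug.

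**4. Size for a completer mean.** Let k of 18 children per dose stop and go unmeasured.

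Overstatement = H_stay − [(18 − k) × H_stay + k × H_stop] / 18 = (k/18) × (H_stay − H_stop)

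The values of H are assumptions.

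| k | H_stay | H_stop | Overstatement |
|---|---|---|---|
| 3 | 1.50 | 1.0 | 0.083 |
| 3 | 1.25 | 1.0 | 0.042 |
| 3 | 1.50 | 1.1 | 0.067 |
| 3 | 1.25 | 1.1 | 0.025 |
| 1 | 1.50 | 1.0 | 0.028 |
| 1 | 1.25 | 1.0 | 0.014 |
| any | 1.0 | 1.0 | 0 |

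Standard error at n = 15: 0.15 / √15 = 0.039. With H_stop = 1.0, three stoppers give about 1.1 to 2.2 standard errors (0.042/0.0387 and 0.083/0.0387). One stopper gives less than one.

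**5. Power if the stoppers are measured.** With k = 3, H_stay = 1.50 and H_stop = 1.0, the mean over 18 is 1.417 and the SD is √(0.15² + (3/18)(15/18)(0.5²)) = 0.239. Power remains > 0.9999. The cost is bias and interpretation, not power.

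**The case against.** The strongest reply is that 9.1.1 does not promise what its first clause suggests. The same paragraph removes withdrawals and missing-data events, so it can be read as counting poorly adherent children who stay in the study, and those children are measured. Section 7.1 agrees with that reading. This stands to the extent that 9.1.1 is inconsistent in itself and 7.1 is not the sole cause. It does not settle 7.1 against 7.2.1, which conflict under either reading.

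A reader might go further in four ways that the documents do not support:

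- *Non-compliant children never have a Month 12 height.* Only definitive discontinuation before the Month 12 window has this effect. Section 6.4 responds to poor compliance first with training and support, and 7.1 expects discontinuation to be rare.
- *The primary result is a completer analysis.* That fits the protocol's 9.4.2 ANOVA of Month 12 change. The SAP's main analysis is a mixed model on the full analysis set that uses earlier visits.
- *A bias of 0.04 to 0.08 is to be expected.* Three of 18 is the all-cause allowance, and includes losses that no amendment could recover. A reference growth rate for stoppers also assumes no benefit from months on drug.
- *Section 7.2.1 contradicts 7.1 for everyone.* It clearly covers those who ask to stop, and less clearly those whom the investigator stops.

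It is also fair to object that rewriting the 7.1 sentence alone would not change the main result, because SAP 6.1.1.1 would discard the extra heights. That is correct, and it is why the SAP must change with the protocol.

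**Conclusion.** The concern holds as a conflict between sections that needs to be reconciled. Sites have opposing instructions on whether Month 12 height is collected after drug is stopped, and the estimand and the SAP each take both sides on whether such data count.

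The size cannot be established from the documents. The figure of 0.04–0.08 is a ceiling for a completer mean. It assumes that all three allowed losses per dose are recoverable stoppers at H = 1.0 and that stayers are at H = 1.25–1.50. One stopper per dose gives 0.014–0.028, below the standard error of 0.039. On this model there is no bias under the null, so the calculation shows no false-positive risk. The mixed model would use the stoppers' earlier visits, but its Month 12 estimate for them is hypothetical rather than observed. Correction is warranted despite the uncertain size, because the lost measurement cannot be recovered and 7.2.1 already requires the follow-up for some of these children.

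**What to change.** 1. Reconcile 7.1 with 7.2.1 so that participants who stop study intervention, and have not withdrawn consent for follow-up, attend the remaining anthropometry visits, at minimum Month 12.
2. Reconcile Protocol 9.1.1, SAP 2.1.1, SAP 6.1.1.1 and SAP Appendix 1 so that these heights enter an analysis that matches an effect regardless of compliance.
3. State how heights are handled after a prohibited growth-affecting treatment is started. Section 7.1 also stops drug in that case, and wider follow-up would bring those heights into the data.
4. If the sponsor prefers to keep the hypothetical strategy as primary, remove the compliance wording from 9.1.1 and its copy in the synopsis, and use the collected heights in a supplementary analysis. The conflict between 7.1 and 7.2.1 must still be resolved.

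The cost is a short protocol amendment, matching SAP edits, and a few extra anthropometry visits for the small number of children who stop drug. When drug should be stopped is not at issue, and no change to those reasons is proposed.
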